We describe all study measures in detail in the study design and procedures sections below and they appear in our appendices. Below is a brief summary of assessments. Purchasing Survey: After obtaining permission from caregivers, a survey will be administered to students after they have made a food or beverage purchase at a school store. The survey will assess participants nutrition knowledge and label awareness, recall, and use, and trust in label information. Frequency of school store visits and sociodemographic characteristics (e.g., age, sex, race/ethnicity, grade level, and height and weight) will also be assessed (see Appendix B for survey). Beverage Frequency Questionnaire: Participants will also complete a beverage frequency questionnaire to assess their consumption of different types of beverages. This questionnaire will be based on the BEVQ-15, a survey instrument that has been validated as an effective tool used to capture changes in beverage consumption. (1-4) (see Appendix E for BEVQ-15). For each beverage category, the questionnaire assesses frequency of consumption and volume typically consumed. (see Appendix D for adapted questionnaire).

Group Modifications

Describe necessary changes that will or have been made to the study instruments for different groups.

None of the survey questionnaires will differ across randomly assigned groups. Regarding the schools that will be enrolled in the study, pairs of matched private/public schools will be randomized to 1 of 3 labeling conditions

Method for Assigning Subjects to Groups

Describe how subjects will be randomized to groups.

Individual participants will not be randomly assigned to groups. Instead, randomization will occur at the school level. Nine schools will be participating in this research and randomization will be stratified based on whether a school is public (n = 6) or private (n = 3). The Penn research team will use a random number generator to randomize schools to one of three labeling conditions, and the Guatemala team will implement the labels based on the randomization assignment.

Administration of Surveys and/or Process

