
Study duration

We anticipate it will take the entirety of the six week data collection period to survey all 1500 adolescents. It will take 5-10 minutes for each participant to complete the survey. We aim to implement the warning labels in school stores by May 2018 and will complete the data collection by the end of June 2018.

Resources necessary for human research protection

Describe research staff and justify that the staff are adequate in number and qualifications to conduct the research. Describe how you will ensure that all staff assisting with the research are adequately informed about the protocol and their research related duties. Please allow adequate time for the researchers to conduct and complete the research. Please confirm that there are adequate facilities for the research.

Characteristics of the Study Population

Target population

To be eligible for the survey component of this project, participants must be: 1) Between 12-18 years or older; 2) Be a currently enrolled student at one of the enrolled schools 3) Have made a purchase at the school store.

Subjects enrolled by Penn Researchers

0

Subjects enrolled by Collaborating Researchers

1500

Accrual

The schools participating in this study will enable us to easily recruit students shopping at the school stores. With a sample size of 1500 (500 per labeling condition), this study is powered to detect small mean differences between the conditions. Specifically, if all three conditions differ by only .21 standard deviations, there is an 82% chance that we would find all differences to be significant.

Key inclusion criteria

To be eligible for the survey component of this project, participants must be: 1) Between 12-18 years or older; 2) Be a currently enrolled student at one of the enrolled schools 3) Have made a purchase at the school store.

Key exclusion criteria

Individuals not meeting the inclusion criteria above will be excluded. Those who will not or cannot give assent will also be excluded from the study. No one will be excluded on the basis of sex or race

Vulnerable Populations

Children Form

Pregnant women (if the study procedures may affect the condition of the pregnant woman or fetus) Form

Fetuses and/or Neonates Form

Prisoners Form

Other

None of the above populations are included in the research study

The following documents are currently attached to this item:

Vulnerable Populations (inclusionofchildren.doc)

Populations vulnerable to undue influence or coercion

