Subjects will not be financially compensated for their participation. However, students will be offered a small prize (e.g., school supplies like pens or pencils) as a token of appreciation for their participation.

Study Procedures

Suicidal Ideation and Behavior

Does this research qualify as a clinical investigation that will utilize a test article (ie- drug or biological) which may carry a potential for central nervous system (CNS) effect(s)?

No

Procedures

Research assistants will be stationed at the school stores during the heaviest traffic times (between 10:00am and 1:30pm and 2:30pm and 3:30pm) Monday to Friday and will invite adolescents to participate in the survey after they make a purchase at the school stores. Only after confirming that a student has permission to participate will the survey be administered. They will be offered a small prize (e.g., school supplies like pens or pencils) as a token of appreciation. After the adolescent has provided verbal consent, a research assistant will record the item(s) purchased (type of food/beverage) along with brand, quantity, size, and price. We will also assess frequency of school store visits and sociodemographic characteristics (e.g., age, sex, race/ethnicity, grade level, and height and weight). We will recruit 1500 students (between 12 and 18 years old) to answer a brief 5-10 minute survey after making a purchase at the school store. Nine schools will be participating in this research and randomization will be stratified based on whether a school is public (n = 6) or private (n = 3). The Penn research team will use a random number generator to randomize schools and the Guatemala team will implement the labels based on the randomization assignment (see Appendix F for label designs). In this six-week study, we will receive purchasing data from the schools during two weeks without labels, two weeks when labels are displayed, and two weeks after labels have been removed. Studying purchases after the labels have been removed will enable us to understand whether the labels are educating children over time or whether they primarily alter behavior by being a salient reminder at the point of purchase.

The following documents are currently attached to this item:

There are no documents attached for this item.

Deception

Does your project use deception?

No

Analysis Plan

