include 100% juice). Frequencies and percentages will be used to describe categorical variables such as percent of students purchasing a sugary drink. Medians and interquartile ranges will be reported for continuous variables that exhibit skewness. Data will be descriptively summarized overall and by labeling strategy. All outcomes will be analyzed at the purchase level. The mean volume of sugary drinks at each two-week period will be modeled among the calorie label, text label, and graphic label arms by a linear regression model including intervention arm, two-week period, interactions of period and intervention arm and type of school (private or public) as independent variables. We will conduct exploratory analyses to examine whether usual frequency of sugary drink intake (high versus low) and biological sex moderate label effects. Examining only aggregate sales data could lead to incorrect inferences. Therefore, complementary individual-level survey data on purchases will also be collected. This aggregate/individual-level data combination will improve inferences about label effects. Although stratification by school type guarantees this variable will be balanced across our intervention arms, we are including it as a covariate in the model because it will enhance the precision of estimating intervention effects, as it explains variability in the outcome. The effectiveness of the interventions will be tested by evaluating the null hypothesis that the coefficients of the interactions of period and intervention are 0, indicating no change in the difference in volume of sugary beverages purchased across intervention arms from baseline. To account for clustering of purchases within schools, test statistics will be corrected using the variance inflation factor (VIF) as determined by the estimated intraclass correlation coefficient (ICC) for within school correlation. Primary and secondary outcomes in the calorie, text-based warning label, and graphic warning label arms will each be compared to one another. A Bonferroni-holm correction will be applied to control for multiple comparisons. We do not expect substantial missing data due to the point-of-sale technology we are using. The primary analysis will examine changes in labeled (sugary) and non-labeled beverages. Secondary analyses will examine changes for the following specific beverage categories: sugar-sweetened cola, sugar-sweetened sports drinks, sugar-sweetened lemonades/iced teas/juices, artificially-sweetened drinks (e.g., Diet Coke), milk, 100% fruit juice, unsweetened coffee/tea, and bottled water. For the survey data, we will conduct similar linear regression analyses to compare total mean kcals purchased among intervention arms.

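### The protocol's single-ICC variance inflation factor is mis-specified for a within-school period-by-arm interaction; it usually makes the test conservative, by an amount the documents do not allow to be fixed

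*Protocol*

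**What the plan says.** All of the following comes from the protocol's Analysis Plan unless another section is named.

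- **Unit and model.** "All outcomes will be analyzed at the purchase level". The model for the primary outcome is given as: "linear regression model including intervention arm, two-week period, interactions of period and intervention arm and type of school (private or public) as independent variables". There is no school term and no school-by-period term.
- **Test.** Label effectiveness is judged by "evaluating the null hypothesis that the coefficients of the interactions of period and intervention are 0".
- **Clustering.** "test statistics will be corrected using the variance inflation factor (VIF) as determined by the estimated intraclass correlation coefficient (ICC) for within school correlation". No VIF formula, cluster size, ICC value or between-period correlation is given, and no reference distribution is named.
- **Repeated observation.** Under Procedures, purchasing data come from "two weeks without labels, two weeks when labels are displayed, and two weeks after labels have been removed", in the same schools throughout.
- **Clusters.** Nine schools (six public, three private) are randomised to three conditions, so three per arm if allocation is equal.

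The SAP (Description of data; Statistical analysis) specifies something else as primary: a two-period difference-in-differences in two schools, one per condition. It mentions no ICC or VIF and gives no method for standard errors.

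**The concern.** The usual design effect, 1+(m-1)ICC, was made for comparing cluster means between arms, where every source of between-cluster variance adds to the error. The protocol's tested coefficient is different: it is a change within each school, compared across arms. A school that always sells more sugary drink per purchase than another contributes nothing to the error of that change. Only variation in how a school's level moves from one fortnight to the next does.

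A single ICC does not separate the two parts. If much of the school variance is stable over six weeks, which is plausible with the same stores and largely the same students, the VIF overcharges. Confidence intervals for the primary comparison are then too wide, p-values too large, and a real label effect could be missed. With only nine schools there is little precision to spare.

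**Working it through.** **The plan's own figure.** The only power figure is in the protocol's Accrual section: 82% to find all differences, with conditions 0.21 SD apart and 500 surveyed students per condition. It reproduces: a two-sample comparison at alpha 0.05/3 gives 0.823, and simulating all three pairwise tests with Holm gives 0.825. Both treat students as independent. The figure concerns the survey sample, so it does not bear on the VIF. No document states a standard error, ICC or VIF for the interaction.

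**Notation.** Total variance 1; k=3 schools per arm; m purchases per school and period; rho = ICC within a period; r = correlation between a school's effects in two periods. Here k follows from the protocol under equal allocation, while m, rho and r are assumptions.

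**Variance of one interaction contrast** (two arms, baseline against one later period):

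- Actual: (4/k) × [(1-rho)/m + rho(1-r)]. The stable part, rho × r, has cancelled.
- VIF-corrected, with the usual formula: (4/k) × [1+(m-1)rho]/m.
- Ratio of standard errors: sqrt{ [1+(m-1)rho] / [(1-rho) + m × rho × (1-r)] }.

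At r=0 the denominator becomes 1+(m-1)rho and the ratio is exactly 1. For any r above 0 it exceeds 1.

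**Worked case: m=1,500, rho=0.01, r=0.8.**

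- Actual: (4/3) × (0.00066 + 0.00200) = 0.00355, SE 0.0596.
- VIF: (4/3) × (15.99/1,500) = 0.01421, SE 0.1192.
- Ratio 2.00.

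**VIF-corrected SE divided by actual SE:**

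| m | ICC | r=0 | r=0.5 | r=0.8 | r=0.9 | r=1 |
|---|---|---|---|---|---|---|
| 56 | 0.01 | 1.00 | 1.10 | 1.19 | 1.22 | 1.25 |
| 500 | 0.01 | 1.00 | 1.31 | 1.73 | 2.01 | 2.46 |
| 500 | 0.05 | 1.00 | 1.39 | 2.09 | 2.74 | 5.23 |
| 1,500 | 0.01 | 1.00 | 1.37 | 2.00 | 2.53 | 4.02 |
| 1,500 | 0.05 | 1.00 | 1.41 | 2.18 | 3.00 | 8.94 |

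The value 56 is 1,500/(9 × 3), the survey count spread evenly over schools and periods; it serves as a low case for m. Simulation with three schools per arm, m=500 and ICC 0.05 agrees with the formula: 0.99, 1.41, 2.08, 2.77 and 5.15 for the same five values of r.

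**Other readings of the sentence.** At m=500 and rho=0.05, a per-period m combined with an ICC pooled over periods gives a ratio of 0.60 at r=0. An ICC taken only from a stable school intercept gives 0.20 at r=0. The direction therefore depends on the unstated definitions of m and ICC.

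**Type I error.** Simulating the VIF test with nine schools, an estimated per-period ICC, m=1,500 and an assumed 1.96 cut-off gives 0.5% at ICC 0.01 and 0.3% at ICC 0.05 when r=0.8, and 2.2% at ICC 0.01 when r=0.5. It passes 5% (7.3%) only at r=0. A comparison of school-level changes on 6 df holds 5%.

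**Power, as illustration only.** With m=1,500, r=0.8 and an interaction of 0.21 SD, power is 35% with the VIF and 1.96 against 83% with the actual error on 6 df at ICC 0.01, and 7% against 61% at ICC 0.02. The 0.21 SD is borrowed from the survey sample, and the Holm correction is left out.

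**The case against.** The strongest reply is that the size of the error is not in the documents. That is correct. A reader might infer that the primary standard error is wrong by a factor of two or more as a matter of fact. The documents do not support this: at 500 to 1,500 purchases, a ratio of 2 needs r of roughly 0.8 to 0.9; at r=0.5 it is about 1.4, and with little data per school it is never reached. Even the formula 1+(m-1)ICC is the customary reading of an unspecified VIF.

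A reader might also infer a second harm, that a normal cut-off with nine schools would overstate certainty. The chance that |t| on 6 df exceeds 1.96 is 9.8%, but that applies to a correctly scaled school-level standard error, not to one that the VIF has already widened. The simulation above shows a conservative test at r=0.5 and 0.8. Nor does either document name 1.96 or a normal reference.

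Finally, a reader might take this VIF to govern the SAP's primary test. The SAP never invokes it, and its design has two schools rather than nine. That the SAP states no standard-error method is a separate gap; it does not carry the protocol's rule across.

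What survives is the mismatch itself: the sentence prescribes an error term that suits the interaction only if a school's periods are uncorrelated.

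**Conclusion.** The point stands for the protocol's nine-school analysis, as a mis-specified clustering correction. Under the usual formula with m and ICC defined consistently, the test is usually conservative. With ICC 0.01 to 0.05 and 500 to 1,500 purchases per school and period, the standard error is about 1.3 to 1.4 times too wide at r=0.5 and 1.7 to 2.2 times at r=0.8, and more if school effects are steadier. It is at most about 1.25 times too wide with 56 purchases at ICC 0.01. These sizes rest on assumed m, ICC and r.

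The SAP's primary analysis is a different case. With one school per condition, 2 schools minus 2 conditions leaves zero school-level degrees of freedom. Neither an ICC nor a school-by-period variance can be separated from the effect.

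**What to change.** **Protocol, Analysis Plan.** Replace the VIF sentence with one of these:

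1. Compute mean ounces of sugary drink per purchase for each school and period, take each school's change from baseline, and compare arms on that change. Use a t reference on school-level residual degrees of freedom: 9 schools minus 3 arms = 6, or 5 if the change is also adjusted for school type. State that schools are weighted equally.
2. Fit a mixed model with random school and random school-by-period effects and a small-sample degrees-of-freedom method.

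Keep the Holm correction across pairwise comparisons.

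**SAP, Statistical analysis.** This repair cannot be carried over. State that with one school per condition no ICC or school-by-period variance can be estimated, and that the reported standard errors therefore do not reflect school-level variation. This makes the limit plain but does not remove it.

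**Cost.** Wording in both documents and a short change to the protocol's analysis code. No new data are needed.

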have shopped at one of the participating stores will qualify to participate. We will use the communication channel each school prefers (e.g., e-mail, printed letters sent home with students) to send permission letters to caregivers (see Appendix A). The letters will explain that their children may be asked to complete a short survey after making a purchase at the school store. Caregivers who wish to refuse participation can call a number provided in the permission letter. All students whose caregivers did not withdraw will be eligible to participate in the survey. Permission letters will be sent two weeks before data collection. Adolescents who have made a purchase from the school store will be asked if they want to complete a short survey; verbal assent must be obtained prior to enrollment (see Appendix C for oral consent script). School Store Setting: Nine schools will be participating in this research and randomization will be stratified based on whether a school is public (n = 6) or private (n = 3). The Penn research team will use a random number generator to randomize schools and the Guatemala team will implement the labels based on the randomization assignment. Each pair of matched private/public schools will be randomized to 1 of 3 labeling conditions: 1) calorie label (control); 2) text warning labels; or 3) graphic warning labels displaying amounts of sugar (see Appendix F). The warning label language will be translated into Spanish before the labels are implemented in the school stores. In this six-week study, we will receive purchasing data from the schools during two weeks without labels, two weeks when labels are displayed, and two weeks after labels have been removed. Warning Label Survey: During the intervention weeks, we will survey approximately 1500 adolescents after they have made a purchase at the school store. We will stratify recruitment to ensure approximately half of the 1500 surveyed students (n=750) are enrolled in public school and half (n=750) are enrolled in private school. Adolescents will be asked if they want to participate in a short, 5-10 minute survey. They will be offered a small prize (e.g., school supplies like pens or pencils) as a token of appreciation. The survey will include constructs that map onto our conceptual model of label effects, such as nutritional knowledge, label awareness, and trust of information on nutritional labels (see Appendix B for survey questions). We will also administer a beverage intake questionnaire (see Appendix D). This questionnaire has been validated among children and adolescents (42,43) Demographic Information: During the survey, we will ask participants to provide basic demographic information including age, sex, race/ethnicity, grade level, and height and weight (see Appendix B for demographic questions). Sales Data: We will collect sales data by setting up a point of sale system in each school store. This system will allow us to collect sales data from each store that will include a row for each purchase made at the school store, including the date of the transaction and the type of food or beverage sold (e.g., diet soda, lemonade) along with the item brand, size, quantity, and price. We will also record the presence and type of food/beverage marketing in the store.

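### Optional gain: for pairwise comparison of three arms on one contrast, Shaffer's steps can replace Holm's within the same 5% familywise bound, once the family is named

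*Protocol*

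**What the plan says.** The relevant text is in the protocol's Analysis Plan. On the comparisons: "Primary and secondary outcomes in the calorie, text-based warning label, and graphic warning label arms will each be compared to one another". On multiplicity: "A Bonferroni-holm correction will be applied to control for multiple comparisons". The hypothesis tested is "the null hypothesis that the coefficients of the interactions of period and intervention are 0". The Design section gives three periods: "two weeks without labels, two weeks when labels are displayed, and two weeks after labels have been removed". Three arms and three periods give four interaction coefficients, that is, two post-baseline contrasts for each pair of arms.

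The Analysis Plan does not say which hypotheses form the Holm family. It also names more than one drink group: "The primary analysis will examine changes in labeled (sugary) and non-labeled beverages". Neither the familywise level nor the sidedness is stated.

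The Accrual section gives the only power statement: "With a sample size of 1500 (500 per labeling condition), this study is powered to detect small mean differences between the conditions", and then "if all three conditions differ by only .21 standard deviations, there is an 82% chance that we would find all differences to be significant".

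The SAP (Description of data; Statistical analysis) bases its primary analysis on two randomised schools, one per condition, and tests one interaction coefficient per outcome. It has no three-arm comparison and names no multiplicity procedure.

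**The concern.** Holm tests the ordered p-values against 0.05/3, 0.05/2 and 0.05. It makes no use of logical links between hypotheses. Three pairwise equalities among three arms are linked: if one pair differs, at least one other pair must differ too. The middle step at 0.025 allows for two true nulls remaining after a correct rejection, and that cannot happen within such a family.

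What is at stake is power for the second rejection. The case most affected is one where both warning labels differ from the calorie label but not from each other. The result would then rest on both control comparisons being significant, and the second of them faces the stricter threshold.

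**Working it through.** **Inputs.** Accrual section: 500 per arm, 0.21 SD, stated power 82%. Analysis Plan: all three pairs, Holm. Assumed, because not stated: familywise 0.05, two-sided. The Accrual figures are taken as independent students with no clustering.

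**1. The protocol's own figure.** The standardised difference for one pair is 0.21 / √(2/500) = 0.21 / 0.06325 = 3.32 SE.
- One pair at 0.05/3 (critical value 2.394): power = Φ(3.32 − 2.394) = 82.3%.
- Arm means 0, 0.21, 0.42 SD, three correlated z tests with Holm's steps, all three rejected (simulation): about 82.6%.
- The same with plain Bonferroni for all three: 65.1%.

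The first two both reproduce 82%, and both rest on a family of three comparisons. The second also matches the wording about finding all differences.

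**2. Possible numbers of true nulls.** For three pairwise equalities the count is 3 (all equal), 1 (two equal, one different) or 0 (all different). It cannot be 2. After a correct first rejection at most 1 remains.

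| Step | Holm | Shaffer |
|---|---|---|
| 1 | 0.05/3 = 0.0167 | 0.05/3 = 0.0167 |
| 2 | 0.05/2 = 0.025 | 0.05/1 = 0.05 |
| 3 | 0.05 | 0.05 |

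No Shaffer threshold is below Holm's, so every Holm rejection is kept.

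**3. Power at 500 per arm, no clustering (simulated).**

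| Arm means (SD) | Event | Holm | Gain with Shaffer |
|---|---|---|---|
| 0, 0.21, 0.42 | all three rejected | about 82.6% | about 0.1 point |
| 0, 0.21, 0.21 | both control comparisons rejected | 77.3% | 6.6 points, to 83.8% |

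In the first row the outer pair, at 2 × 3.32 = 6.64 SE, is nearly always rejected first. Shaffer then helps only if both remaining p-values fall between 0.025 and 0.05, which is rare. In the second row it helps whenever the smaller control p-value passes 0.0167 and the other lies between 0.025 and 0.05.

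No ICC is given, so the effect of clustering can only be illustrated. If the effective sample were 250 per arm (an assumption), the equally spaced case goes from 34.2% to 35.5% and the two-equal case from 37.4% to 46.4%.

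**4. Actual familywise error.**
- Global null: 4.4% with either procedure.
- Two warnings equal, 3.32 SE from control: 3.8% with Holm, 5.0% with Shaffer.
- Two warnings equal, 2.8 SE from control (an illustrative effect, not from the documents): 3.2% and 4.8%.

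**5. If the family spans both post-baseline contrasts.** Each contrast has 0, 1 or 3 true nulls, so two contrasts together can have 0, 1, 2, 3, 4 or 6. Five is impossible. Shaffer's divisors are 6, 4, 4, 3, 2, 1 against Holm's 6, 5, 4, 3, 2, 1. Only the second threshold moves, from 0.05/5 = 0.010 to 0.05/4 = 0.0125.

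Applying the three-pair steps separately to each contrast would not control this larger family. With the contrasts assumed independent, error under the global null would be 1 − (1 − 0.044)² = 8.6%, against 4.5% for Holm over all six.

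**The case against.** The strongest objection is that the protocol never fixes the family. The argument that only one true null can remain needs a family of three, and the text also brings in two post-baseline contrasts and more than one outcome. A rewrite that adds limits by outcome and period could give up control the authors intended. This stands as a condition on the fix: the family must be named first. It does not remove the point. The three-pair family is the better supported reading, because the 82% is reproduced with exactly three comparisons. That support is indirect, since the Accrual statement concerns the survey sample and the primary outcome comes from sales data.

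The second objection is that the gain depends on the scenario. The objectives include whether the graphic label beats the text label, so equality of the two is not the authors' planning case. In the equally spaced version of their own scenario the gain is negligible. This stands.

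A reader might infer three stronger things that the documents do not support:
- **That using Holm is a mistake.** It is valid, and the stated 82% is reached with it.
- **That the middle step costs power and protects nothing.** Only the 5% bound is unchanged; actual error rises towards it, as step 4 of the working shows.
- **That the trial's main result is at risk.** The SAP's primary analysis has two conditions and one coefficient per outcome, so there is no second step to relax.

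**Conclusion.** This is an optional improvement to the protocol's three-arm analysis, not the correction of an error. Within a family of three pairwise comparisons on one outcome and one contrast, Holm's middle threshold is stricter than the 5% bound requires, and Shaffer's steps recover the lost power. The benefit ranges from about 0.1 point (equally spaced arms) to about 6.6 points (both warnings equal) at 500 per arm and 0.21 SD. These sizes assume a two-sided familywise 0.05 and no clustering. In a six-hypothesis family the improvement is confined to one step. No test in the SAP's primary analysis changes.

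**What to change.** If the three-arm analysis stands, amend the multiplicity sentence in the protocol's Analysis Plan to:
1. State the familywise level and sidedness.
2. Name the family as the three pairwise arm comparisons within each outcome and each post-baseline contrast.
3. Replace Holm by Shaffer's sequentially rejective steps: the smallest p-value against 0.05/3, then the remaining two in order against 0.05, stopping at the first failure.

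If the sponsor intends one family across both post-baseline contrasts, use divisors 6, 4, 4, 3, 2, 1 over the six hypotheses instead. Do not apply the three-pair steps to each contrast separately in that case.

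The cost is a sentence or two and one changed threshold, with no new data and no design change. The price in error terms is that the actual familywise rate moves closer to 5% when exactly one null is true. Keeping Holm is also acceptable, but the family should still be named.
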